4.1. Primary Endpoint

Volume of aspirated cyst fluid as a function of estimated maximal volume based on pre-aspiration EUS measure of cyst diameter (s) (% aspiration of total estimated volume).

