4.2. Secondary Endpoints

Safety Endpoint

- Occurrence, severity and relatedness of adverse events to the needle and procedure.

Other Endpoints

- b. Extent of cyst aspiration as measured by reduction of maximal cyst diameter before and after FNA (converted to volume by standard geometric formulation).
- c. Successful echoendoscopic fine needle aspiration of PCL, defined as complete cyst aspiration or collection of aspirate adequate to perform two standard assays: cytology and carcinoembryonic antigen (CEA).

NOTES: Endpoint c) success is defined as:

- complete aspiration, defined as reaching a final cyst maximal diameter of less than 5mm attained with a maximum of 3 needle passes; in the case of a multilocular cyst, complete aspiration of the largest locule is required,

or

- collection of aspirate adequate to perform two standard assays: cytology and CEA, attained with a maximum of 3 needle passes

Total aspirate volume should be 3cc or more. In cases where less than 3cc of aspirate is obtained but cytology and CEA assays can be adequately completed, the primary endpoint is considered to have been met. Aspirate handling procedures are provided in Section 7.4 below.

- d. Ability to reach and penetrate the PCL, stratified by route of access and PCL location.
- e. Number of EUS-FNA needles and EUS-FNA needle passes* used.
- f. Time needed for aspiration for each pass and time from first needle pass in[†] to last needle pass out[‡].

DEFINITIONS:

**Needle pass* -- from needle insertion through needle removal outside the cyst lumen, but not including needle repositioning within a single or multi-compartment cyst.

Note: A maximum of 3 needle passes are allowed, after which the EUS-FNA procedure will be considered failed.

[†]*Time of first needle pass in* -- time of the first needle puncture into the cyst lumen.

[‡]*Time of last needle pass out* -- time of removal of needle outside the cyst lumen at the end of the last fluid aspiration from a single or multi-loculated cyst, or after 10 seconds of failed attempt to aspirate fluid after the last needle re-positioning in a single or multi-compartment cyst.

- g. Ease of needle passage in and out of echoendoscope and quality of needle visualization inside the cyst, categorized as *Excellent, Very Good, Good, Fair, and Poor*.

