9.1. Study Hypothesis and Sample Size Calculation

Sample size was calculated based on assumptions for the primary endpoint as well as for secondary endpoint c):

9.1.1. *Primary endpoint considerations:*

The study hypothesis states that for either of the 19 G Flex and 19 G Arms, the volume of actual aspirated cyst fluid as a ratio (%) of estimated maximal volume is superior by at least 10% compared to that of the 22 G Arm.

The study investigators provided the following experience-based estimate of the primary endpoint (aspirate volume as % of max volume based on EUS image of the cyst):

Figure 4 – Hypothesis Generating References (Primary Endpoint)

Site Investigator	Mean Volume Ratio (%) for 19G and 19Flex needles	Mean Volume Ratio (%) for 22G needles
Investigator 1	80%	50%
Investigator 2	90%	70%
Investigator 3	90% Unilocular cysts, 50% Multi-locular	80%

	cysts, 80% Blended mean	
Investigator 4	90%	90%
Investigator 5	90%	50%
Investigator 6	85%	65%

From the above table, bootstrap method with 10,000 resamples yielded an estimated mean of 67.44% and standard deviation of 15.29% for 22G, and a mean of 85.9% and standard deviation of 4.67% for 19G/19G Flex.

The assumption was made that the mean of the “control group”, namely the 22G arm, will be 67% with a standard deviation of 15.29%.

Two null hypotheses are made:

- H_{01} : Mean volume ratio of 19 G Flex Arm and 22 G Arm are the same
- H_{02} : Mean volume ratio of 19 G Arm and 22 G Arm are the same

The alternative hypothesis is:

- H_1 : Mean volume ratio of 19 G Flex/19G Arm is superior to 22 G Arm

If 50 patients are enrolled in the 19 G Flex Arm and 25 patients each in the 19 G and 22 G Arm, the study will have 90% conjunctive power to detect the rejection of both null hypotheses to demonstrate superiority of the mean volume ratio of 19 G Flex Arm and 19 G Arm to that of 22 G Arm by 10% or more. Thus, a minimum of 100 patients (50+25+25=100) are required.

9.1.2. Secondary endpoint c) considerations:

The study hypothesis states that the EUS-FNA 19 G Flex needle is superior to the EUS-FNA 22 G standard and 19 G standard needles in the secondary endpoint c) measure, which requires access or adequate aspirate volume for two standard assays expected from successful EUS-FNA procedures in PCL assessment indications.

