Exclusion Criteria	
 
1. Cysts in which FNA is not indicated based on review by the clinician, including potential concern of blood vessel location relative to the cyst.
 
2. Requirement for anticoagulation using clopidogril, warfarin, or other long acting antiplatelet agents (with the exception of aspirin) that cannot be safely stopped according to institutional guidelines.
 
3. Standard contraindications for EUS.
 
4. Known pancreatic pseudocyst.
 
5. Pregnancy.
 

Statistical Methods and Sample Size	
The sample size of this study was computed based on the following assumptions on the primary endpoint, as well as for the secondary endpoint c):
 
Primary endpoint considerations:
 
 
• The volume of actual aspirated cyst fluid as a function of estimated maximal volume either in 19 G or 19 G Flex Arm is superior by at least 10% compared to the 22 G Arm, detected with 90% conjunctive power, using multiple comparison Hochberg's step up method.
 
• Requires 50 subjects in 19 G Flex Arm, and 25 subjects each in 22 G and 19 G Arms.
 
 
Secondary endpoint c) considerations:
 
 
• Superiority of EUS-FNA success rate in 19 G Flex Arm by 16% or more compared to both the success rate of the 19 G Arm and the 22 G Arm, detected with 80% conjunctive power, using multiple comparison Hochberg's step up method.
 
• Requires 121 subjects in 19 G Flex Arm, and 61 subjects each in 22 G and 19G Arm, rounded up
 
 
The final sample size was considered to be the maximum of required sample sizes of the above stated two endpoints to make sure that the both endpoints are properly powered, namely 250 subjects.

A flow chart illustrating the study design is provided in **Figure 1** below.

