### 3 ENDPOINT ANALYSIS

#### 3.1 Primary Endpoint

##### 3.1.1 Hypotheses

The primary endpoint is “Volume of aspirated cyst fluid as a function of estimated maximal volume based on pre-aspiration EUS measure of cyst diameter (s) (% aspiration of total estimated volume).”

Analysis Approach:

% aspiration of total estimated volume is calculated overall and for each arm (19 G Flex, 22 G, 19 G) and/or a combination of arms such as 19G Flex and 19G, for each and combined morphologic characteristics, and for no salvage subjects. If there is multilocular morphology, the primary endpoint is calculated for measurements of the largest locule.

Valid Data Sources:

- Procedure Form: sections “PCL Characteristics” and “Post-Aspiration Assessment”

Valid Data Points:

- Morphology: Unilocular (Pre-aspiration EUS measures)
  - Maximal diameter (long axis) (mm)
  - Perpendicular measurement (short axis) (mm)
- Morphology: Multilocular (Pre-aspiration EUS measures)
  - Measurements of the largest locule
    - Maximal diameter (long axis) of the largest locule (mm)
    - Perpendicular measurement (short axis) of largest locule (mm)
- Total volume of aspirate (Post-aspiration assessment)

Formula:

$$\% \text{ aspiration of total estimated volume} = \frac{A-B}{A} \times 100 \%$$

Volume is computed using the standard geometric formula  $\left(\frac{4}{3}\pi R^3\right)$  where R is half the long axis. The volume unit is in cc. “A” is calculated by the image during pre-procedure measurements. “B” is calculated by the image during post-procedure measurements.

Hypotheses:

$H_{0i}: \mu_i - \mu_0 \leq 0$  Versus  $H_{1i}: \mu_i - \mu_0 > 0$  for  $i=1, 2$ ;

where  $\mu_0$  is mean volume percentage of 22 G Arm,  
 $\mu_1$  is mean volume percentage of 19 G Flex Arm, and  
 $\mu_2$  is mean volume percentage of 19 G Arm.

Superiority by 10% or more is deemed clinically significant.

The multiple comparison Hochberg's step up method will be used.

The analysis population for the primary endpoint will be the Intent to Treat and Per-protocol analysis sets.

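### SAP 3.1.1 names aspirated fluid as the primary endpoint, but its only formula measures shrinkage on the image, so aspirate volume never enters the endpoint value

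*SAP*

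**What the plan says.** Protocol 4.1 defines the primary endpoint as "Volume of aspirated cyst fluid as a function of estimated maximal volume based on pre-aspiration EUS measure of cyst diameter", expressed as a percentage. SAP 3.1.1 repeats this definition, and its list of valid data points includes "Total volume of aspirate (Post-aspiration assessment".

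The same SAP section then gives one formula, (A−B)/A × 100%. Each volume is a sphere, (4/3)πR³, with R half the long axis. A comes from the pre-procedure image, and B "is calculated by the image during post-procedure measurements". For multilocular cysts the largest locule is used. Neither document gives any other formula for the primary endpoint. SAP 3.1.3 tests the arm means of this percentage with Hochberg's procedure.

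The planning values concern the aspirate ratio. Protocol 9.1.1 describes the investigators' estimates as "aspirate volume as % of max volume based on EUS image of the cyst", and the sample-size text in SAP 1 refers to "The volume of actual aspirated cyst fluid as a function of estimated maximal volume".

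Secondary endpoint b (Protocol 4.2, SAP 5.1.1) is "Extent of cyst aspiration as measured by reduction of maximal cyst diameter before and after FNA", converted to volume.

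**The concern.** The endpoint that is named and the endpoint that is computed are different variables. The mismatch runs both ways: aspirate volume is a listed input that the formula does not use, and the post-procedure diameter that B requires is not a listed input.

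If SAP 3.1.1 is programmed as written, the confirmatory test is run on something close to secondary endpoint b, differing in its percentage scale and its explicit largest-locule rule, and the protocol's primary endpoint is never tested. If the programmer follows the endpoint text and the data-point list instead, another variable is tested. The primary result would then depend on how one person resolves the section. The stated power would also be attached to a variable for which nothing was planned.

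**Working it through.** **1. The plan's own power figure.** Inputs from SAP 3.1.2: means 67 (22 G), 77 (19 G) and 77 (19 G Flex); SDs 15.29, 4.67 and 4.67; n = 25, 25 and 50; one-sided α = 0.05; Hochberg. Both hypotheses are rejected when the larger p-value is at most 0.05.

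- 19 G v 22 G: SE = √(15.29²/25 + 4.67²/25) = 3.197; 10/3.197 − 1.645 = 1.483; power 0.931.
- 19 G Flex v 22 G: SE = √(15.29²/25 + 4.67²/50) = 3.128; 10/3.128 − 1.645 = 1.552; power 0.940.
- Jointly, by simulation (400,000 trials, unequal-variance statistic of SAP 3.1.3): conjunctive 0.916 and global 0.927 with the normal reference; 0.905 and 0.916 with a Welch t reference. The plan states 0.901 and 0.912.

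The figure reproduces on its inputs. The question is which variable those inputs describe, and Protocol 9.1.1 says the aspirate ratio.

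**2. The formula written out.** With long axis L₀ before and L₁ after, both as sphere diameters, (A−B)/A = 1 − (L₁/L₀)³. No term depends on the fluid collected. Aspirate volume enters only through the rule in SAP 7.4 that it must exceed zero for membership of the per-protocol set.

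**3. Do the two measures coincide?** Assumptions: the cyst is an ellipsoid whose third axis equals its short axis; all fluid removed is captured (V); A is the SAP's long-axis sphere. For a 30 mm long axis, A = (π/6) × 3³ = 14.14 cc. A 30×20 mm cyst holds (π/6) × 3 × 2 × 2 = 6.28 cc.

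| Long × short axis, mm | V, cc | (A−B)/A | V/A |
|---|---|---|---|
| 30×30 → 15×15 | 12.37 | 87.5% | 87.5% |
| 30×20 → 15×10 | 5.50 | 87.5% | 38.9% |
| 30×20 → 30×5 | 5.89 | 0% | 41.7% |
| 30×20 → 25×5 | 5.96 | 42.1% | 42.1% |

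The measures agree for a sphere that shrinks evenly. Otherwise they may agree or may differ by more than 40 points in either direction. These are illustrations and do not estimate the typical gap.

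**4. What a bare substitution of aspirate volume would do.**

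- Shape error cancels in (A−B)/A under proportional shrinkage, but not in V/A. A fully emptied 30×20 mm cyst scores 6.28/14.14 = 44% (third axis = short) or 9.42/14.14 = 67% (third axis = long). With a two-axis A, the second row of the table would give 5.50/6.28 = 87.5%.
- Protocol 7.2 has every locule accessible in the same pass aspirated, while SAP 3.1.1 takes A from the largest locule only. Assuming fully emptied spherical locules of 20 mm (4.19 cc) and 15 mm (1.77 cc), the score is (4.19 + 1.77)/4.19 = 142%.

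**The case against.** The best defence is that B is the residual volume, so A−B estimates what was removed and the formula is an image-based version of the named endpoint. It handles shape well, as step 4 shows. This does not reconcile the section. B is explicitly an image measurement, aspirate volume is listed as an input, and image-based reduction already has its own place as secondary endpoint b.

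A second defence is that power is ample. With the plan's SDs at 61/121/61, the SEs are 2.047 (19 G) and 2.003 (19 G Flex), so 10/SE − 1.645 is 3.24 and 3.35 and conjunctive power is about 99.9%. That reserve is real, but it still rests on SDs given for the aspirate ratio.

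A reader might also infer more than the documents support:

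- **That power is lost.** Assumed common SDs of 15.29, 20, 25 and 30 at 61/121/61 give 97%, 84%, 64% and 48%. These SDs are not specific to image shrinkage and would lower power for the aspirate ratio equally. The supportable statement is that power is not documented for the variable tested.
- **That the measures agree only for spherical cysts.** The last row of the table is a counterexample.
- **That near-100% scores after complete aspiration reveal an error.** Complete aspiration means "reaching a final cyst maximal diameter of less than 5mm", and eligible cysts measure at least 13 mm, so such cysts score above 1 − (5/13)³ = 94.3%. A collapsed cyst should score near 100%; the figure shows nothing wrong.
- **That the comparison is biased or type I error is inflated.** One formula applies to all arms, and nothing in the documents shows either.

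**Conclusion.** SAP 3.1.1 is wrong as written and should be corrected before analysis. The definition and data-point list describe the aspirate ratio, as do Protocol 4.1 and the planning text; the only formula computes image shrinkage. The confirmatory variable is therefore not uniquely specified and, read literally, is not the protocol's primary endpoint.

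That conclusion rests on the text alone. The size of the divergence cannot be derived from the documents; the illustrative gaps depend on the assumed ellipsoids and full capture of fluid. They show only that the choice of variable can matter on a scale well above the 10-point target. The need to reconcile the section is firm. The documents do not compel a particular geometry for A or a particular multilocular rule.

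**What to change.** In SAP 3.1.1, set the primary endpoint to 100 × aspirate volume (cc) obtained with the randomised needle before any salvage, divided by A, and delete B. Move (A−B)/A to SAP 5.1.1 as the formula for secondary endpoint b, using the final diameters recorded under Protocol 7.4, and report it as supportive of the primary.

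State in SAP 3.1.1:

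1. **Geometry of A.** Either keep the long-axis sphere or use both listed axes with the third-axis assumption given; run the other as a sensitivity analysis.
2. **Multilocular cysts.** Reconcile the largest-locule rule with an aspirate total drawn from all accessible locules. The aggregate size recorded under Protocol 8.3.1 is one option, but it may include locules that were never reached. Report unilocular cysts separately, as the section's breakdown by morphology already allows; one investigator's planning estimate (Protocol 9.1.1, Figure 4) was "90% Unilocular cysts, 50% Multi-locular".
3. **Salvage.** Say how salvaged subjects enter the ITT analysis if the CRF holds only one aspirate total.

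The cost is SAP wording and programming, because aspirate volume, both pre-aspiration axes, aggregate size and final diameters are already to be recorded. Two points must be checked on the CRF: whether aspirate before salvage is recorded separately, and which axes define aggregate size. If aspirate before salvage is not separate, the endpoint cannot be computed as defined for salvaged subjects, and item 3 becomes essential.

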7.2. Needle Puncture and Aspirate Requirements

The following procedural rules will be followed:

- a. Initial needle puncture with stylet in place (with time stamp). Remove stylet and apply 10cc suction. If no aspirate visible in syringe lumen after 5 seconds of suction: reposition needle and re-apply suction. If no aspirate after 5 seconds of suction- lesion classified as FNA failure. Switch to salvage method.

- b. If aspirate visible within syringe lumen, hold suction until no additional material accumulated for 10 seconds. If cyst completely collapses, note final time stamp. If cyst is not completely collapsed, then repositioning is allowed until all cyst locules have been punctured, and no additional fluid is obtained for 10 seconds. Note final time stamp. If cysts is not completely collapsed after attempts, above, note final maximal and perpendicular diameter.
- c. In case of a multi-compartment, loculated lesion, all locules accessible with the same needle pass will be aspirated, with priority to the largest locule. In cases where a locule is positioned in front of another along the axis of the needle, the one most proximal to the needle tip should be fully aspirated before accessing the locules located in a more distal position.
- d. In the event that cyst components cannot be reached without repuncture, remove needle completely from cyst (note time stamp for pass completion). Repuncture for pass 2 (or more) as needed until criteria (see "b" above) for complete aspiration or failure is met.
- e. If maximal cyst diameter is > 5mm after efforts described in "b" above, cyst aspiration is considered "failed." Switch to salvage method (19 Flex, if first method was not 19 Flex).

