7.4. Post-Procedure Handling of Cyst Aspirate

- a. Record final cyst maximum diameter and perpendicular diameter.
- b. Record total volume of cyst aspiration by suctioning all material, including what is in the needle lumen, into the syringe, inverting it, and removing air.
 - If sample volume is > 3cc, send 2cc to chemistry laboratory for CEA. Send remainder to cytology lab.
 - If sample volume is < 3cc, divide the sample into two aliquots guided by volumetric requirements of the local cytology and chemistry labs.
 - Sequential portions of the aspirate will be used for the two assays as follows:
 - o First aliquot (preferably at least 1cc) – Cytology
 - o Second aliquot (preferably at least 1cc) – CEA
 - o All remaining fluid is to be added to the first aliquot and sent for cytology

- In case the total aspirate volume is insufficient to satisfy local cytology and chemistry lab requirements, then the aliquot order outlined above should be used to prioritize which subset of assays will be performed.
- In cases in which the aspirate volume is more than 1 cc but less than 3 cc, the first cc should be sent for cytology and the remainder should be sent for CEA. Some laboratories may have the ability to perform CEA assays on less than 1 cc of fluid for assay.
- In cases in which the aspirate volume is less than 1 cc, the aspirate will nevertheless be sent for cytology.

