### 3.1.2 Sample Size

The sample size was estimated based on the following assumptions:

Design parameters:

One-sided Type I Error=0.05

Multiple comparison method= Hochberg's step up

Rejection region=Right tail

Treatment parameters:

Arm	Mean volume percentage	Standard deviation	Sample size per group
22G	67	15.29	25
19G	77	4.67	25
19GFlex	77	4.67	50

Overall power:

Global (reject any  $H_{0i}$ ): 0.912

Conjunctive (reject all  $H_{0i}$ ): 0.901

Given the above assumptions, a total sample of 100 subjects will be required where 50 subjects will be in 19 G Flex arm, and 25 subjects in the 19 G and 22 G arms respectively.

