## 4 GENERAL STATISTICAL METHODS

### 4.1 Analysis Sets

The Intent-to-treat (ITT) cohort will consist of all randomized subjects, namely subjects who signed the ICF, met all eligibility criteria (see note below), were randomized to one of three study arms, and experienced echoendoscope insertion and attempted EUS-FNA procedure. Subjects in this cohort, independent of whether or not the EUS-FNA was successful, will be counted towards the enrollment ceiling. Any adverse events occurring or resulting from a treatment attempt will be collected.

NOTE:

Exclusion criteria #1 may be documented after a subject was randomized and the EUS procedure was started. In such cases, the subject will be excluded from the study and no longer be a part of the ITT cohort.

The Modified Intent-to-treat population will consist of ITT population with salvage, namely the subjects with 19G + Salvage, 22G + Salvage, and 19G Flex+ Salvage.

The per-protocol (PP) cohort will consist of the subset of the ITT subjects in whom the target lesion could be reached and EUS-FNA yielded any aspirate, used the assigned needle, and there were no major protocol deviations.

All endpoints will be analyzed for all subjects and stratified by EUS-FNA needle type (by randomization arm) for the ITT analysis set. Similarly, primary and selected secondary endpoints will be analyzed for the PP analysis set.

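### The SAP does not say whether the primary endpoint's after-measurement is taken before or after salvage; read literally it is after, which biases the needle comparison, and the no-salvage calculation cannot replace it

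*SAP*

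**What the plan says.** SAP 3.1.1 computes percent aspiration as (A−B)/A, with volumes from a sphere on the long axis. A comes from the pre-procedure image; B "is calculated by the image during post-procedure measurements". For multilocular cysts the largest locule is used. The endpoint is to be calculated overall, by arm, for combinations of arms, by morphology, "and for no salvage subjects". The analysis sets for the primary endpoint are ITT and per-protocol.

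Protocol 7.2 sets the sequence. Under item a, a needle that draws nothing after one repositioning is a failure and salvage follows. Under item b, if the cyst has not collapsed after all attempts, the final maximal and perpendicular diameters are noted. Item e begins "If maximal cyst diameter is > 5mm after efforts described in" item b; such a cyst counts as failed and salvage follows. Under 7.3, 22 G and 19 G failures should be salvaged with 19 G Flex, and 19 G Flex failures with 19 G or 22 G. The salvage attempt follows 7.2 again.

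Protocol 7.4, the post-procedure section, comes next. It records final diameters and instructs sites: "Record total volume of cyst aspiration by suctioning all material, including what is in the needle lumen". SAP 4.1 adds: "The Modified Intent-to-treat population will consist of ITT population with salvage". The SAP assigns no analysis to that population.

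**The concern.** The primary question is what the randomised needle achieves. A 22 G patient with residual fluid receives a second aspiration with 19 G Flex in the same session. If B is measured after that, the 22 G result includes 19 G Flex aspiration, and the trial compares two-needle sequences, two of which end with the same needle. Two programmers could follow SAP 3.1.1 in good faith and report different primary results. Restricting to unsalvaged subjects does not recover the comparison, because salvage is triggered by the outcome itself.

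**Working it through.** **Inputs.** Test: "One-sided Type I Error=0.05", Hochberg over two comparisons with 22 G (SAP 3.1.2). Target: "Superiority by 10% or more is deemed clinically significant" (SAP 3.1.1). Planned 22 G mean: "will be 67% with a standard deviation of 15.29" (Protocol 9.1.1). Planned 19 G and 19 G Flex mean 77, SD 4.67 (SAP 3.1.2). Minimum diameter 13 mm, applied to the largest locule if multilocular (Protocol 5.2). Salvage trigger: residual above 5 mm (Protocol 7.2e). The effect of salvage is not given anywhere and is assumed below.

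**1. The plan's own power.** SAP 3.1.2 states conjunctive power 0.901 and global power 0.912 at 25/25/50 (22 G/19 G/Flex). Simulating 200,000 trials with two unequal-variance comparisons sharing the 22 G arm gives 0.913 and 0.925 with the normal reference of SAP 3.1.3, and 0.904 and 0.915 with a Welch t reference. The stated figures are reproduced. With the normal reference, conjunctive power at 61/61/121 is 0.999. All of this presumes a 10-point difference between needles.

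**2. Which image is B?**
- Pointing to post-salvage: Protocol Figure 3 puts salvage in the procedure column, and 7.4 records final diameters and a single total volume after the salvage section.
- Pointing to pre-salvage: 7.2b notes diameters before the 7.2e switch, which itself needs a diameter, and a with-salvage population is defined separately from ITT.
- Settling nothing: salvage repeats 7.2, so 7.2b can yield one final diameter per needle. A dry failure under 7.2a goes to salvage without reaching 7.2b. The SAP does not say which value is B.

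**3. If B is post-salvage.** The planned mean residuals are 100−67 = 33 (22 G) and 100−77 = 23 (19 G, Flex). Let salvage remove a fraction f22 or fF of an arm's mean residual:

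difference = (77 + 23·fF) − (67 + 33·f22) = 10 − 33·f22 + 23·fF.

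With equal f this is 10(1−f). Conjunctive power below keeps the planned SDs.

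| f (assumed) | Difference | Power, n=100 | Power, n=243 |
|---|---|---|---|
| 0 | 10 | 0.91 | 0.999 |
| 25% | 7.5 | 0.72 | 0.97 |
| 50% | 5.0 | 0.42 | 0.75 |
| 75% | 2.5 | 0.17 | 0.29 |

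Unequal f: with f22 = 50% and fF = 25%, the difference is 10 − 16.5 + 5.75 = −0.75. It exceeds 10 only if fF is more than 33/23 = 1.43 times f22.

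**4. No-salvage subjects.** On the SAP formula, percent aspiration = 100 × [1 − (d_post/d_pre)³]. If every residual above 5 mm is salvaged, the unsalvaged have d_post of 5 mm or less:

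| Smallest d_pre | Lowest possible value | Largest possible gap between arm means |
|---|---|---|
| 13 mm | 94.31% | 5.69 points |
| 20 mm | 98.44% | 1.56 points |
| 30 mm | 99.54% | 0.46 points |

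**5. How many patients this touches.** If complete cysts score at least 94.31% and incomplete ones at least 0%, the complete share is at most 67/94.31 = 0.710 in 22 G and 77/94.31 = 0.816 in the 19 G arms. At least 29% and 18% would therefore be due for salvage.

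**6. How firm is the ceiling in step 4?** Suppose a share q of unsalvaged 22 G subjects are failures left without salvage, with mean aspiration m, while completed cysts in both arms average between 94.31% and 99%. A 10-point gap needs q = 10/(completed mean − m): 10–11% if m = 0, and 20–23% if m = 50.

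**The case against.** The strongest reply is that this is an unclear definition, not a wrong rule. A reader might infer that the SAP prescribes a post-salvage B. It does not: the formula never mentions salvage, Figure 3 lists the index aspiration and salvage as separate items, and 7.2b and the Modified ITT favour a pre-salvage ITT value. That stands, and the point is put as an ambiguity whose literal reading is harmful.

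A reader might also infer that the no-salvage calculation is the only alternative, or that a 10-point difference there is impossible by construction. Neither is supported. The primary analysis sets are ITT and per-protocol, and the no-salvage calculation is one of several listed breakdowns, with no hypothesis test attached. The ceiling needs full adherence to salvage, where 7.3 says only that it should be done, and it needs the image formula. The protocol's endpoint is aspirated volume over estimated volume, and the SAP lists total aspirate volume as a data point; on that scale the 94.3% floor does not apply. The per-protocol set does not resolve the timing: a salvaged patient also used the assigned needle first, and if the set is read as excluding salvage it too is selected on outcome.

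On size, it is tempting to say that 33% and 23% must be incomplete (100 minus the planned means). That ignores that a complete cyst may score 94.3%; the bounds are 29% and 18%. Applying a normal curve to the protocol's SDs would suggest that nearly everyone is incomplete, but those SDs were bootstrapped from six investigators' estimated means and do not describe spread among patients. The power losses are also conditional: at n = 243 and f = 25% power is still 0.97, and if every residual shrank by the same fraction the SDs would shrink too.

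Finally, the Procedure CRF is not among the documents. One can say only that the protocol and SAP do not ask for a pre-salvage aspirate volume, not that none is captured.

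**Conclusion.** The concern holds as an unfixed definition of the primary endpoint. The literal reading credits salvage aspiration to the randomised arm; the apparent intention is the opposite, and the SAP does not decide between them. The main harm is a biased effect estimate rather than a certain loss of power. The planned 10 points become 10(1−f) under an assumed equal f, and unequal f could cut the difference further or reverse it. The documents give no value for f.

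The no-salvage result cannot stand in for the ITT comparison. Its 5.7-point ceiling assumes that every residual above 5 mm is salvaged and that the sphere formula is used. The figures of at least about 29% and 18% due for salvage assume values between 0 and 100% on the image scale, whereas the planning means were elicited as aspirate volume over estimated volume. This should be settled before the final analysis.

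**What to change.** - In SAP 3.1.1, define B, and aspirate volume wherever it is used, as the value after the randomised needle's last pass and before any salvage puncture, in all ITT subjects.
- State that aspiration is 0% where the randomised needle did not reach the cyst or drew nothing.
- In Protocol 7.2 and 7.4 and on the Procedure CRF, record diameters and volume before salvage and again after it. Use the second set only for the Modified ITT, and say in the SAP what analysis that population receives.
- Label the no-salvage result descriptive and non-comparative.

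The cost is SAP wording, a few CRF fields and a short extra measurement in salvaged patients, with no added patients or procedures. Volumes must be noted per needle before the fluid is pooled, so that the 7.4 aliquot rules are unaffected. A pre-salvage volume not recorded during the procedure cannot be recovered afterwards.
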